6.2.7.1.3 Key Secondary OS Analysis

OS will be summarized using Kaplan-Meier method, and the descriptive statistics of median, 25% and 75% percentiles along with their 95% CIs will be calculated. It will be based on the ITT analysis set. The supportive data listings will also be provided.

In addition to the quartile summary from Kaplan-Meier method, Kaplan-Meier estimates will be provided for the survival rates at 3, 6, 9, and 12 months along with their 95% CIs. Additionally, a comparison will be conducted between trilaciclib and GC only. The two-sided p-value from a Cox proportional hazard model will be presented, the model includes treatment and stratification factors as fixed effects. The HR between the two treatment groups, together with its 95% CIs will be presented.

6.2.7.1.4 Multiplicity Adjustments

The clinical trial evaluates the objectives defined in terms of the comparison of trilaciclib + E/P/A versus placebo + E/P/A on the primary and key secondary myelosuppression efficacy endpoints in [Sections 5.1.1 and 5.1.2](#).

The multiplicity problem includes the following 5 hypotheses of no effect:

- Hypothesis H_1 . Comparison of trilaciclib + E/P/A versus placebo + E/P/A for duration of severe (Grade 4) neutropenia in Cycle 1.
- Hypothesis H_2 . Comparison of trilaciclib + E/P/A versus placebo + E/P/A for occurrence of severe (Grade 4) neutropenia.
- Hypothesis H_3 . Comparison of trilaciclib + E/P/A versus placebo + E/P/A for all-cause dose reductions in the MAHE composite.
- Hypothesis H_4 . Comparison of trilaciclib + E/P/A versus placebo + E/P/A for occurrence of RBC transfusions on/after Week 5 on study.
- Hypothesis H_5 . Comparison of trilaciclib + E/P/A versus placebo + E/P/A for occurrence of G-CSF administration.

These 5 hypotheses can be grouped into 3 families:

- Family 1 (F_1) includes the hypothesis H_1 .
- Family 2 (F_2) includes the hypothesis H_2 .
- Family 3 (F_3) includes the hypotheses H_3 , H_4 , and H_5 .

[figure not shown]
The 1-sided p-values for these 5 comparisons will be used for the multiple testing procedure.

A Hochberg-based gatekeeping procedure will be utilized to control the global familywise error rate across the 5 null hypotheses in the strong sense at a 1-sided $\alpha=0.025$ level, and it satisfies the positive dependence condition at the 1-sided setting. The procedure is built using the mixture methodology developed in Dmitrienko and Tamhane (2011) and accounts for the logical restrictions among the 5 hypotheses displayed in

Figure 2 by performing multiplicity adjustments in three steps. The logical restrictions can be achieved by defining the parallel set and serial set for each individual hypothesis based the tree-structured procedure introduced by Dmitrienko et al (2007).

- Step 1. The trilaciclib vs placebo comparisons for Family 1 (hypothesis H_1) are performed using a truncated version of the Hochberg procedure. The truncation parameter γ is set to 0.
- Step 2. The trilaciclib vs placebo comparisons for Family 2 (hypothesis H_2) are performed using a truncated version of the Hochberg procedure if H_1 is significant in Step 1. The truncation parameter γ is set to 0.
- Step 3. The trilaciclib vs placebo comparisons for Family 3 (hypotheses H_3 , H_4 , and H_5) are performed using the regular Hochberg test if H_2 is significant in Step 2.

Figure 2 Graphical Display of the Hochberg-based Gatekeeping Procedure

The logical restrictions in the Step 1 and Step 2 contain only one single hypothesis, and the Step 3 has three hypotheses H3, H4, H5, though the testing procedure can be broadly considered as a fixed sequence procedure, its implementation can be performed through the framework of Hochberg-based gatekeeping procedure as described in detail below.

The regular Hochberg test is defined in Dmitrienko et al. (2009) and the truncated Hochberg test is defined in Dmitrienko, Tamhane and Wiens (2008). The decision rules used in the regular and truncated Hochberg tests will be detailed in the following. In general terms, the truncated version of the Hochberg test is defined as a convex combination of the regular Hochberg and Bonferroni tests. An important parameter of the truncated Hochberg test is the truncation parameter γ which ranges between 0 and 1. If the truncation parameter γ is set to 0, the truncated Hochberg test simplifies to the Bonferroni test. On the other hand, if the truncation parameter γ is set to 1, the truncated Hochberg test is identical to the regular Hochberg test. The truncated Hochberg test satisfies the separability condition (Dmitrienko, Tamhane and Wiens, 2008) if the truncation parameter γ is strictly less than 1. This condition ensures that in each step of the testing algorithm the error rate can be transferred to the next step provided at least one comparison is significant in the current step without inflating the overall type I error rate (Huque, 2016; FDA, 2017).

Testing algorithm

This section describes the implementation of the Hochberg-based gatekeeping procedure. The testing algorithm relies on the general approach to defining multistage gatekeeping procedures based on mixtures of multiple tests proposed in Dmitrienko and Tamhane (2011).

Decision rules

The aforementioned 5 hypotheses are grouped into 3 families:

- Family 1 (F_1) includes the hypothesis H_1 .

- Family 2 (F_2) includes the hypothesis H_2 .
- Family 3 (F_3) includes the hypotheses H_3 , H_4 , and H_5 .

Using more compact notation, the families are defined as follows:

$$F_1 = \{H_i, i \in N_1\}, F_2 = \{H_i, i \in N_2\}, F_3 = \{H_i, i \in N_3\}.$$

where the index sets are defined as $N_1 = \{1\}$, $N_2 = \{2\}$, $N_3 = \{3,4,5\}$. Let t_i and p_i denote the test statistic and 1-sided p-values associated with the hypotheses, respectively. Let α denote the global familywise error rate, i.e., one-sided $\alpha = 0.025$.

Consider the closed family associated with Families 1, 2 and 3, i.e., a family of all non-empty intersections of the five hypotheses. Each intersection will be identified by an index set

$$I \subseteq N = \{1, \dots, 5\}$$

(note that the empty set is excluded). For example, the index vector $I = \{1, 2, 5\}$ corresponds to the intersection of the hypotheses H_1, H_2 , and H_5 .

To construct the Hochberg-based gatekeeping procedure that controls the global familywise error rate in the strong sense at an α level, an α -level test needs to be defined for each intersection in the closed family. The multiple test and associated p-value for an intersection are computed in two steps.

Step 1: Define p-values for subset intersections

Consider an intersection corresponding to the index set $I \subseteq N$ and define the index sets $I_k = I \cap N_k$, $k = 1, 2, 3$. The p-values for the index sets I_1, I_2 , and I_3 are computed as follows:

Let n_1 denote the number of hypotheses included in I_1 and let $m_1 = n_1$. If $n_1 > 0$, the truncated Hochberg p-value is defined using the ordered p-values associated with the hypotheses included in the index set I_1 , denoted by

$$p_{1(1)} \leq \dots \leq p_{1(m_1)}$$

The truncated Hochberg p-value for the index set I_1 is given by

$$p(I_1) = \min_{i=1, \dots, m_1} \frac{p_{1(i)}}{\frac{\gamma_1}{m_1 - i + 1} + (1 - \gamma_1)}$$

Here γ_1 is the pre-specified truncation parameter in Family 1. Choosing a larger value of γ_1 improves the power of comparisons in Family 1, and γ_1 is set to 0.5.

Further, let n_2 denote the number of hypotheses included in the index set I_2 . If $n_2 > 0$, consider the hypotheses in the index set I_2 and remove the hypotheses that are not consistent with the logical restrictions defined in

Figure 2. Let m_2 denote the number of hypotheses remaining in the index set I_2 after this logical restriction operation. If $m_2 > 0$, let

$$p_{2(1)} \leq \dots \leq p_{2(m_2)}$$

denote the ordered p -values for the hypotheses remaining in the index set I_2 . The truncated Hochberg p -value for I_2 is given by

$$p(I_2) = \min_{i=1, \dots, m_2} \frac{p_{2(i)}}{\frac{\gamma_2}{m_2 - i + 1} + (1 - \gamma_2)}$$

where γ_2 is the pre-specified truncation parameter in Family 2, which plays the same role as γ_1 in Family 1, and γ_2 is set to 0.5.

Finally, let n_3 denote the number of hypotheses included in I_3 . If $n_3 > 0$, remove the hypotheses that are not consistent with the logical restrictions defined in

Figure 2. Let m_3 denote the number of hypotheses remaining in the index set I_3 after this logical restriction operation. If $m_3 > 0$, let

$$p_{3(1)} \leq \dots \leq p_{3(m_3)}$$

denote the ordered p -values for the hypotheses remaining in the index set I_3 . The Hochberg p -value for I_3 is given by

$$p(I_3) = \min_{i=1, \dots, m_3} \frac{p_{3(i)}}{m_3 - i + 1}$$

Step 2: Define overall p -value

The overall p -value for the intersection corresponding to the index set I is computed by combining the p -values associated with the index sets I_1, I_2 , and I_3 . Consider the following three scenarios:

- If $n_1 > 0$, the overall p -value is found using the following mixing function:

$$p(I) = \min \left(\frac{p(I_1)}{b_1}, \frac{p(I_2)}{b_2}, \frac{p(I_3)}{b_3} \right)$$

where $b_1 = 1$, $b_2 = b_1(1 - f_1)$, $b_3 = b_2(1 - f_2)$ and f_1 and f_2 are computed based on the error rate functions of the truncated Hochberg tests used in Families 1 and 2. These quantities are defined below.

- If $n_1 = 0$ and $n_2 > 0$, the overall p -value is given by

$$p(I) = \min \left(\frac{p(I_2)}{b_2}, \frac{p(I_3)}{b_3} \right)$$

where $b_2 = 1$, $b_3 = b_2(1 - f_2)$.

- If $n_1 = 0, n_2 = 0$ and $n_3 > 0$, the overall p -value is given by

$$p(I) = \frac{p(I_3)}{b_3}$$

where $b_3 = 1$.

The error rate function of the truncated Hochberg test with the truncation parameter γ_k for testing an intersection corresponding to the index set I_k , $k = 1, 2$, is defined as

$$e_k(I_k) = P[p(I_k) \leq \alpha]$$

and $f_k = e_k(I_k)/\alpha$, $k = 1, 2$. It is shown in Brechenmacher et al. (2011) that

$$e_k(I_k) = [\gamma_k + (1 - \gamma_k)|I_k|/n_k]\alpha$$

if the index set I_k is non-empty and $e_k(I_k) = 0$ the index set I_k is empty. Here $|I_k|$ denotes the number of hypotheses included in the index set I_k .

As shown in Dmitrienko and Tamhane (2011), the resulting test for the intersection corresponding to the index set I is an α -level test. This implies that the Hochberg-based

gatekeeping procedure controls the global familywise error rate in the strong sense at a one-sided $\alpha = 0.025$.

Multiplicity-adjusted p-values

Multiplicity-adjusted p -values for the Hochberg-based gatekeeping procedure are computed using the closure principle. For each hypothesis, the adjusted p -value is defined as the maximum over the p -values associated with the intersections in the closed family that include the hypothesis of interest. For example, the adjusted p -value for H_2 is the maximum over the p -values for intersections containing H_2 . The calculations are performed using the decision matrix algorithm, see Dmitrienko and Tamhane (2011).

Regular and truncated Hochberg tests

Consider a general problem of testing m null hypotheses denoted by H_1, \dots, H_m . Let p_1, \dots, p_m denote the associated raw p -values. Further, let $p_{(1)} < \dots < p_{(m)}$ denote the ordered p -values and $H_{(1)} < \dots < H_{(m)}$ denote the hypotheses corresponding to the ordered p -values.

The regular Hochberg test is based on the following testing algorithm:

- Step 1: If $p_{(m)} > \alpha$, accept $H_{(m)}$ and go to Step 2, otherwise reject all null hypotheses and stop.
- Step $i = 2, \dots, m - 1$: If $p_{(m-i+1)} > \alpha/i$, accept $H_{(m-i+1)}$ and go to Step $i + 1$, otherwise reject all remaining null hypotheses and stop.
- Step m : If $p_{(1)} > \alpha/m$, accept $H_{(1)}$, otherwise reject $H_{(1)}$.

The truncated Hochberg test with the truncation parameter γ is based on the following testing algorithm:

- Step 1: If $p_{(m)} > [\gamma + (1 - \gamma)/m]\alpha$, accept $H_{(m)}$ and go to Step 2, otherwise reject all null hypotheses and stop.
- Step $i = 2, \dots, m - 1$: If $p_{(m-i+1)} > [\gamma/i + (1 - \gamma)/m]\alpha$, accept $H_{(m-i+1)}$ and go to Step $i + 1$, otherwise reject all remaining null hypotheses and stop.
- Step m : If $p_{(1)} > \alpha/m$, accept $H_{(1)}$, otherwise reject $H_{(1)}$.

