6.2.7. Efficacy Analyses

All the efficacy variables will be summarized using descriptive statistics by cycle or visit, with the supportive data provided in patient listings. Data will be summarized using descriptive statistics and the between treatment comparison (trilaciclib vs placebo), will be performed only for the primary and secondary endpoints outlined in [Sections 5.1.1 – 5.1.3](#). The comparisons between trilaciclib vs. placebo will be built into the multiplicity adjustment described in [Section 6.2.7.1.4](#), the adjusted one-sided p-values will be reported and be the basis for the study drug efficacy conclusion and claim at the significance level of one-sided 0.025. However, for these comparisons, all statistical tests will be conducted at a two-sided .05 alpha level unless otherwise specified. Where appropriate, model-based point estimates, together with their two-sided 95% CIs will be presented along with the two-sided p-value for the test unless otherwise specified. Graphical presentation of efficacy results will be performed as needed.

Unless otherwise specified, all analyses for the efficacy endpoints will be conducted for the induction treatment period which is defined to be between the date of randomization and the end of the last induction cycle.

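### The printed Hochberg p-value for the key secondary family (H3 to H5) divides where the rest of the SAP section multiplies; coded as printed, it removes the multiplicity adjustment within that family

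*SAP*

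**What the plan says.** All the statements are in SAP Section 6.2.7.1.4 unless noted.

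- **Intended test.** Step 3 says the Family 3 comparisons "are performed using the regular Hochberg test if H_2 is significant in Step 2". Protocol Section 13.5.3.2 specifies the same test for Region 2.
- **Printed p-value for Family 3.** Under Decision rules, after "The Hochberg p -value for I_3 is given by", the expression is the minimum over i of p3(i) / (m3 - i + 1).
- **Truncated p-value for Families 1 and 2.** After, for example, "The truncated Hochberg p -value for I_2 is given by", the ordered p-value is divided by gamma/(m - i + 1) + (1 - gamma). The section also states that at gamma = 1 "the truncated Hochberg test is identical to the regular Hochberg test".
- **Step-wise rule.** Following "The regular Hochberg test is based on the following testing algorithm", the largest p-value is compared with alpha, the i-th largest with alpha/i and the smallest with alpha/m.
- **Use of the result.** Multiplicity-adjusted p-values "for the Hochberg-based gatekeeping procedure are computed using the closure principle", each being the maximum over all intersections that contain the hypothesis. SAP Section 6.2.7 says "the adjusted one-sided p-values will be reported and be the basis for the study drug efficacy conclusion and claim", at one-sided 0.025.
- **Error control.** Strong familywise control at one-sided 0.025 is claimed across all five hypotheses.

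**The concern.** The section gives two executable definitions of one confirmatory test, and they run in opposite directions. A Hochberg intersection p-value should be inflated to allow for the number of hypotheses; the printed Family 3 line shrinks it. The line lies directly on the path to the adjusted p-values that decide the key secondary claims.

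If it were programmed literally, more claims could be made on dose reductions, transfusions and G-CSF than the step-wise rule allows. Choosing between the two definitions after unblinding would be hard to defend, because one of them always gives at least as many claims as the other.

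**Working it through.** **Inputs.** One-sided alpha = 0.025; Families {H1}, {H2}, {H3, H4, H5}; the p-value formulas, mixing weights, error rate function and closure rule of SAP 6.2.7.1.4. The documents give no correlations between the tests, so the values 0, 0.3, 0.5 and 0.8 are assumptions.

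**1. What the other two statements imply.** At gamma = 1 the truncated denominator is 1/(m - i + 1), so the p-value is (m - i + 1) × p(i). For m = 3 this is the minimum of 3p(1), 2p(2) and p(3). The step-wise rule compares p(3) with 0.025, p(2) with 0.025/2 and p(1) with 0.025/3, which is the same thing. The printed line gives the minimum of p(1)/3, p(2)/2 and p(3).

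**2. The stated 0.025 is reproduced with the multiplied form.** Running the full closure over all 31 intersections, the multiplied form agreed with H1, then H2, then step-wise Hochberg in all 5,000 random sets of p-values. With H1 and H2 rejected and independent tests, familywise error is 0.0250, 0.0250 and 0.0248 for one, two and three true nulls in Family 3.

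**3. The gate.** Families 1 and 2 hold one hypothesis each, so f = gamma + (1 - gamma) × 1/1 = 1 for any gamma. The weight on Family 3 is therefore 0 whenever H1 or H2 is in the intersection. The SAP does not say how to treat division by a zero weight. Reading it as infinite (ignored in the minimum), or removing H3 to H5 under the logical restrictions, gives the same result and the gate holds. For example, p2 = 0.2 with all other p-values at 0.0001 gives adjusted p of 0.2 for H2 to H5.

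**4. What the printed line does inside Family 3.** For any two or three of the hypotheses, the printed p(I3) is at most p(1)/m, which is below every raw p-value in the set. The maximum over intersections is then always reached at the single hypothesis itself. Hence adjusted p for Hk = max(p1, p2, pk) for k = 3, 4, 5. This was exact in all 5,000 random sets, with gamma 0 or 0.5.

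**5. Size of the three-way intersection test.** As printed, it rejects when p(1)/3 ≤ 0.025, that is p(1) ≤ 0.075. Under independence the probability is 1 - 0.925³ = 20.9%. The closure argument needs this to be 2.5%.

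**6. Familywise error with the gate passed.** As printed under independence: 1 - 0.975³ = 7.3% with three true nulls and 1 - 0.975² = 4.9% with two. Correlated cases and Hochberg are from 4 million simulated normal triples per correlation.

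| Assumed correlation | 3 nulls, printed | 3 nulls, Hochberg | 2 nulls, printed | 2 nulls, Hochberg |
|---|---|---|---|---|
| 0 | 7.3% | 2.5% | 4.9% | 2.5% |
| 0.3 | 6.8% | 2.4% | 4.8% | 2.5% |
| 0.5 | 6.3% | 2.3% | 4.5% | 2.4% |
| 0.8 | 4.9% | 1.9% | 3.9% | 2.2% |

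**7. An example where the claims differ.** Let H1 and H2 pass with very small p-values, and let the Family 3 raw p-values be 0.020, 0.022 and 0.30.

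- Hochberg: 3 × 0.020 = 0.060, 2 × 0.022 = 0.044, 1 × 0.30 = 0.30. Adjusted values are 0.044, 0.044 and 0.30, so there is no claim.
- Printed: the three-way value is 0.020/3 = 0.0067 and the pairs give 0.010 or 0.011, so the adjusted values stay at 0.020, 0.022 and 0.30. There are two claims.

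**The case against.** **The fault may come from reading the PDF.** A lost 1/ in the denominator would produce exactly this expression. One could add that the truncated p-value formulas carry (1 - gamma) where the step-wise truncated rule has (1 - gamma)/m, which might suggest that fractions were lost throughout the block. The first point stands and cannot be settled from the text. The second is weak: with one hypothesis in each of Families 1 and 2, m is 1 and the two forms coincide, so no term need be missing, and the nested fraction in those formulas survived.

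**The intent is clear.** Step 3 and the step-wise rule name and describe Hochberg correctly, so a competent programmer would probably implement it. This stands, and it is why the point is conditional on literal coding. It does not make the conflicting line harmless. The independent program validation in SAP Section 6.1.1 looks for valid methods, which might catch the fault, but also for consistency with the plan, which code following the printed line would satisfy.

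**The 7.3% is an extreme case.** It needs literal coding, both primaries rejected, three true nulls and independence. Protocol Tables 8-2 and 8-3 tie both G-CSF use and dose reductions to neutrophil counts, so positive correlation is more plausible. This stands too. At a correlation of 0.8 the error is still 4.9% with three true nulls and 3.9% with two.

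**Conclusion.** The concern holds for the SAP as read. The Family 3 p-value is inverted relative to two other statements in its own section. If it is programmed literally, strong control at one-sided 0.025 fails for the key secondary endpoints. Familywise error is then between 4.9% and 7.3% with three true nulls and between 3.9% and 4.9% with two, over assumed correlations from 0.8 down to 0, given that H1 and H2 have been rejected. With a single true null there is no inflation.

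H1, H2 and the serial gate are unaffected, provided that terms with zero weight are ignored. Sample size and power are not involved. Confidence is moderate, because the printed formula has to be confirmed on the source page. It should be corrected before unblinding.

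**What to change.** 1. Check the formula on the source page of the SAP.
2. If it stands as read, replace it with p(I3) = minimum over i of (m3 - i + 1) × p3(i).
3. Validate the program's adjusted p-values against the step-wise Hochberg rule in the same section, including a case such as 0.020, 0.022 and 0.30, where the two forms give different claims.
4. In the same edit, state that terms with zero mixing weight are ignored, and align gamma, which is 0 in Steps 1 and 2 but 0.5 under Decision rules. The gamma mismatch has no numerical effect here, because Families 1 and 2 each hold one hypothesis.

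The cost is one corrected formula, one line of code and one validation check, all of which can be done before unblinding.

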6.2.7.1.5 Robustness of Primary and Key Secondary Efficacy Analyses

A binary response variable (Yes, No) will be analyzed to compare trilaciclib and placebo using stratum-adjusted method to account for ECOG (0 or 1 vs. 2) and brain metastases (Yes vs. No) as the stratification factor. The adjusted proportion difference (trilaciclib vs placebo) and its 95% CIs will be calculated using Cochran-Mantel-Haenszel (CMH) weight outlined in Kim et al. 2013. The two-sided p -value will be calculated using stratified exact CMH method. Additionally, three sets of sensitivity analysis will be conducted to evaluate the robustness of the results from primary or key secondary analyses for a binary response variable (Yes, No).

- (i) For patients who die during the induction treatment period (up to 30 days after last dose in induction period) without experiencing an event, Yes will be assigned to the variable.

- (ii) After the imputation from (i), a worst-comparison analysis will be done to establish a stringent boundary of the treatment effect. Patients who die during the induction treatment period will still be set to Yes, and patients who do not complete 4 induction cycles and do not experience an event will then be imputed. If the patient is from the placebo group, No will be assigned to the variables, Yes will be assigned to the trilaciclib group.
- (iii) After the imputation from (i), a tipping-point analysis (Yan et al., 2009) will be performed by assigning the response to the variable for patients who do not complete 4 induction cycles and do not experience an event.

The tipping-point analysis assumes all possible combinations of numbers of Yes and No for the missing responses (defined as patients without an event who have less than 4 induction cycles) in the trilaciclib and placebo groups. For example, let n_t be the number of randomized trilaciclib patients with missing response and n_c be the number of randomized placebo patients with missing responses. For the trilaciclib patients with missing values, there are $n_t + 1$ possible assumptions for number of No (i.e. 0, 1, 2, ..., to n_t); for the placebo patients with missing values, there are $n_c + 1$ possible assumptions for number of No. Therefore, there are total of $(n_t + 1) \times (n_c + 1)$ possible combination of assumptions for number of No and Yes for the trilaciclib and placebo patients with missing responses. The un-stratified exact CMH method will be performed on the available responses with each of these $(n_t + 1) \times (n_c + 1)$ assumptions and will be summarized. A figure will be presented with points representing each possible combination where the significant p-value 'tips' to greater than a one-sided 0.025, which would represent a change in the study conclusions. Clinical justification will be provided to evaluate whether the assumption is plausible.

A waterfall plot showing the number of induction cycles with SVN will be presented.

DSN for each induction cycle will be presented using descriptive statistics. The primary analysis on DSN defined by Strategy 1 (refer to [Section 6.2.7.1.1](#)) will be repeated on DSN defined by Strategy 3 (refer to [Section 5.1.1.2.3](#)).

Each of the analyses will be repeated using two additional distinct data sets to evaluate the confounding effect of GCSF administration: inclusion of only those patients or cycles who had concurrent GCSF administration; and inclusion of only those patients or cycles who did NOT have concurrent GCSF administration. The "with" and "without" GCSF analyses are subsets of the total number of patients or cycles.

DSN, Strategy 2 (refer to [Section 5.1.1.2.2](#)) endpoint will be summarized using Kaplan-Meier method, and the descriptive statistics of median, 25% and 75% percentiles along with their 95% CIs will be calculated. Additionally, DSN for each cycle will be presented using descriptive statistics.

In addition to the summary from Kaplan-Meier method, the two-sided p-value will be obtained from the stratified Kaplan-Meier method to account for the stratification factors. The hazard ratio (HR) between the two treatments (trilaciclib vs placebo), together with its 95% CIs will be calculated from a Cox proportional hazard model in which treatment and the stratification factors will be included as fixed effects.

For the time (days) to first occurrence of a MAHE event, a graphical display of cumulative incidence will be presented.

The primary and key secondary efficacy endpoints are based on the ITT analysis set, and the analysis will be repeated for the mITT analysis set and PP analysis set.

For RBC transfusions, subsets of subjects with baseline HGB <9 g/L and ≥ 9 g/L will be provided, as well as a summary of the number of units transfused.

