6.2.7.1.2 Key Secondary Efficacy Analyses

Occurrence of RBC transfusions on/after 5 weeks on study is a binary variable and will be summarized using the same method for occurrence of SVN described in [Section 6.2.7.1.1](#) except baseline HGB will be used as a covariate instead of baseline ANC in the modified Poisson model. Also, the offset will be the logarithm transformation of duration of induction treatment period divided by 7 (i.e. week) instead of number of induction cycles, and. An additional sensitivity analysis will look all transfusions during the induction treatment period, and all transfusions with a subset of subjects completing at least 1 cycle.

Occurrence of GCSF administration is a binary variable and will be summarized using the same method for occurrence of SVN described in [Section 6.2.7.1.1](#).

All-cause dose reductions will be analyzed to compare trilaciclib and placebo using a negative binomial regression model to account for the potential over-dispersion. The model includes the stratification factors of ECOG (0 or 1 vs. 2) and brain metastases (Yes vs. No), and treatment as a fixed effect. The logarithm transformation of number of induction cycles will be included as an offset variable in the modeling. The two-sided p-value, aRR (trilaciclib vs placebo) and its 95% CIs will be presented.

The total number of all-cause dose reductions will be summarized descriptively, along with the number of induction cycles, and the event rate per cycle (calculated as the total number of events/total number of induction cycles). The cumulative incidence of events during the induction treatment period will be summarized and presented graphically by cycle.

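### The tipping-point figure marks a changed conclusion at an unadjusted one-sided 0.025, but RBC transfusion (H4) and G-CSF (H5) are decided by Hochberg-adjusted p-values, so an overturned H4 claim can be shown as intact

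*SAP*

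**What the plan says.** SAP 6.2.7.1.5 plans three sensitivity analyses for binary primary and key secondary endpoints, which are severe neutropenia (H2), RBC transfusion on or after Week 5 (H4) and G-CSF administration (H5). The third is a tipping-point grid, run after step (i), which has already recoded event-free deaths during induction as events. The grid covers every count of events among patients with no event and fewer than four induction cycles, separately by arm. On the test: "The un-stratified exact CMH method will be performed on the available responses with each of these" combinations. On the boundary: the figure shows points "where the significant p-value 'tips' to greater than a one-sided 0.025, which would represent a change in the study conclusions".

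The confirmatory rule is elsewhere. Under SAP 6.2.7, "the adjusted one-sided p-values will be reported and be the basis for the study drug efficacy conclusion and claim". SAP 6.2.7.1.4 sets out to "control the global familywise error rate across the 5 null hypotheses in the strong sense at a 1-sided" level of 0.025. H1 and H2 are tested in sequence. H3 (all-cause dose reductions), H4 and H5 then "are performed using the regular Hochberg test if H_2 is significant in Step 2". The p-values for H2, H4 and H5 come from modified Poisson regression with a baseline covariate, the stratification factors and an offset (6.2.7.1.1 and 6.2.7.1.2; for H5, "Occurrence of GCSF administration is a binary variable and will be summarized using the same method for occurrence of SVN").

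**The concern.** A tipping-point display has one job: to show how many unfavourable imputations it would take to lose a claim. It can do this only if its boundary is the boundary at which the claim is lost. Section 6.2.7.1.5 ties its boundary to the study conclusions, yet uses a fixed 0.025. For H4 and H5 the level that decides the claim depends on the other two p-values in Family 3 and can be half or a third of 0.025. In those cases the figure would leave unmarked some combinations that have already overturned the claim, and the result would look more robust than it is.

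The display also uses a different test from the one that produces the claim, so even its starting point need not agree with the confirmatory result.

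**Working it through.** **1. The plan's own figure.** Global one-sided α = 0.025 and Family 3 has m = 3 (SAP 6.2.7.1.4). The regular Hochberg steps there compare the largest p with α = 0.025, the next with α/2 = 0.0125 and the smallest with α/3 = 0.0083. The tipping level of 0.025 is therefore the step-1 level. It is also the level for H2, which is alone in its family, once H1 is rejected.

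**2. Raw critical value for H4.** Let a ≤ b be the p-values of H3 and H5 in order.
- b ≤ 0.025: critical value 0.025, and the plan's boundary is right.
- b > 0.025 and a ≤ 0.0125: critical value 0.0125.
- b > 0.025 and a > 0.0125: critical value 0.0083.

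The same holds for H5 with H3 and H4 as the other two.

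**3. Worked example.** The assumptions are 53 per arm (half of the 106 in SAP 2.3), H1 and H2 rejected, H3 p = 0.04 and H5 p = 0.0001. Here b = 0.04 and a = 0.0001, so the H4 critical value is 0.0125. The exact one-sided p is the hypergeometric lower tail. The Hochberg-adjusted p for H4 is min(2 × p, 0.04) while H4 is the middle p-value, and p itself once it is the largest.

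| Events, trilaciclib vs placebo | Exact p | Adjusted p | H4 claim | Planned figure |
|---|---|---|---|---|
| 2 vs 11 | 0.0075 | 0.0151 | made | no tip |
| 3 vs 11 | 0.0208 | min(0.0416, 0.04) = 0.040 | lost | no tip |
| 4 vs 11 | 0.0461 | 0.0461 | lost | tip |

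One imputed event loses the claim, but the figure reports that it takes two. Modified Poisson without covariates or offset gives the same pattern: 0.0110 at 2 vs 11 (claim made) and 0.0183 at 3 vs 11 (lost).

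**4. A whole grid.** Assume 2 vs 13 events at the start and 6 patients to be imputed per arm, so 7 × 7 = 49 combinations. The exact p exceeds 0.025 in 12, exceeds 0.0125 in 18 and exceeds 0.0083 in 23. The planned figure would miss 18 − 12 = 6 or 23 − 12 = 11 overturned combinations. These counts show direction only.

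**5. Which endpoint is exposed.** Rates are from the earlier first-line study in Protocol 4.3.1.
- RBC transfusion: 2/35 vs 8/37 scales to about 3 vs 11 of 53. The exact p of 0.0208 lies between 0.0125 and 0.025, where the choice of level matters.
- G-CSF: 4/38 vs 24/37 scales to about 6 vs 34 of 53. The p-value is about 1e-8 (exact) or 7e-6 (modified Poisson), far from any boundary before imputation.

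**6. Test mismatch (53 per arm, modified Poisson without covariates or offset).** At 4 vs 12 the exact p is 0.0275 and the Poisson p is 0.0217, on opposite sides of 0.025. At 1 vs 10 they are 0.0040 and 0.0127, on opposite sides of 0.0125. Neither test is uniformly the stricter.

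**7. A dependency inside 6.2.7.1.4.** The critical values above follow the stepwise algorithm introduced by "The regular Hochberg test is based on the following testing algorithm". The decision-rules part of the same section prints the Family 3 intersection p-value as the minimum of each ordered p divided by (m₃ − i + 1). The algorithm implies multiplication. Taken literally, the printed formula leaves every Family 3 adjusted p equal to the raw p, because no intersection can exceed the single-hypothesis value. In the example, H4 at 3 vs 11 would stay at 0.0208. That would agree with the 0.025 tipping level, but it would not be the Hochberg test that the section names.

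**The case against.** The strongest reply is that this is a sensitivity display. No confirmatory decision or type I error rate depends on it. Results for all combinations are to be summarised, so a reader could apply another cut-off. The worst-case comparison in step (ii) is also planned, and plausibility has to be justified clinically. All of that stands, and it limits the harm. It does not rescue the wording, because the SAP itself equates crossing 0.025 with a changed conclusion.

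The un-stratified exact test is also defensible. The grid fixes only counts per arm, so a stratified or covariate-adjusted test would need to know which patients carry the imputed events.

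Three stronger readings are tempting but not supported:
- **That 0.025 is wrong for every endpoint.** It is correct for H2 given H1, and for H4 or H5 when the other two Family 3 p-values are at or below 0.025. With H5 as strong as the earlier study suggests, H4 would face 0.0125 at worst, not 0.0083.
- **That a claim would often appear tipped before anything is imputed.** The grid starts after step (i), so the observed coding is generally not one of its points. How often the two tests disagree at the real starting point cannot be worked out from the documents.
- **That the misplacement is frequent.** It depends on how likely H3 is to fail and how H3 and H4 are correlated, and the documents give neither. The nearest evidence, neutropenia-related dose reductions in the earlier study (p = 0.0033, Protocol 4.3.1), leans towards H3 succeeding, although H3 itself counts all-cause reductions.

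**Conclusion.** The point holds in a limited form. The tipping rule in SAP 6.2.7.1.5 is not the rule that decides H4 and H5, and it can place the boundary too far out when another Family 3 hypothesis fails. The realistic case is RBC transfusion when dose reductions fail: the deciding level is then 0.0125, half the level used in the figure. In the example this is a one-event error, with the claim lost at one imputed trilaciclib event and the figure tipping at two.

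The level argument needs no simulation. It rests on reading the 0.025 in 6.2.7.1.5 as unadjusted, since no adjustment is mentioned there, and on the stepwise Hochberg algorithm governing Family 3. The event counts, the 53 per arm and the H3 and H5 p-values are assumptions for illustration. The correction is worth making before unblinding, but it does not affect the validity of the confirmatory tests.

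**What to change.** 1. In SAP 6.2.7.1.4, reconcile the printed Family 3 p-value formula with the stepwise algorithm. The critical values depend on it.
2. In 6.2.7.1.5, redefine the tip. For each combination, carry the endpoint's one-sided p-value through the gatekeeping procedure with the other hypotheses' observed p-values, and mark a tip when the multiplicity-adjusted p-value exceeds 0.025. For H4 and H5 this is the same as using the Hochberg critical value implied by the other two Family 3 p-values, provided H1 and H2 are rejected.
3. Keep the un-stratified exact test for the count grid if preferred. State in the output whether the grid's starting point, after step (i), agrees with the confirmatory modified Poisson conclusion.

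The cost is a few lines of SAP text and a little more programming before unblinding, with no new data. The downside is that the reported tipping point for H4 may look less favourable.
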